JAMA:	Journal of the American Medical Association
MAR:	Missing at Random
MCAR:	Missing Completely at Random
MCID:	Mean Clinically Important Difference
MEDD:	Morphine Equivalent Daily Dose
MI:	Motivational Interviewing
MNAR:	Missing Not at Random
mPI:	Multiple Principal Investigator
MSD:	Musculoskeletal disorders
NCCIH:	National Center of Complementary and Integrative Health

NDS:	National Data Systems
NIDA:	National Institute on Drug Abuse
NIH:	National Institutes of Health
NLP:	Natural Language Processing
NPCD:	National Patient Care Database
NPM:	Non-Pharmacological Pain Modalities
NRS:	Numeric Rating Scale
OEF:	Operation Enduring Freedom
OHRP:	Office for Human Research Protections
OIF:	Operation Iraqi Freedom
OI&T:	Office of Information & Technology
PACT:	Patient Aligned Care
PEG:	Three-Item Scale Assessing Overall Pain Intensity and Interference
PMC3:	NIH-DoD-VA Pain Management Collaboratory Coordinating Center
PHI:	Personal Health Information
PHQ-9:	Patient Health Questionnaire
PPV:	Positive Predictive Values
PRC:	Protocol Review Committee
PRIME:	Pain Research, Informatics, Multi-morbidities, and Education Center
PT:	Physical Therapy
PTSD:	Post-Traumatic Stress Disorder
QUERI:	VA Quality Enhancement Research Initiative
RCT:	Randomized Controlled Trial
REDCap:	Research Electronic Data Capture
SAE:	Serious Adverse Event
SAMSHA:	Substance Abuse and Mental Health Services Administration
SBIRT:	Screening, Brief Intervention and Referral to Treatment
SBIRT-PM	Screening, Brief Intervention and Referral to Treatment for Pain Management
SCAN-ECHO:	Specialty Care Access Networks-Extension for Community Healthcare Outcomes
SPACE:	Strategies for Prescribing Analgesics Comparative Effectiveness
SUD:	Substance Use Disorder
SVM:	Support Vector Machine
TAU:	Treatment-As-Usual
TBI:	Traumatic Brain Injury
TENS:	Transcutaneous Electrical Nerve Stimulation
UG3:	Phase 1 Exploratory/Developmental Cooperative Agreement activity code
UGH:	Phase 2 Exploratory/Developmental Cooperative Agreement activity code

UC:	Usual Care
VA:	Veterans Affairs
VACHS:	VA Connecticut Healthcare System
VACO:	VA Central Office
VAMC:	VA Medical Centers
VBA:	Veterans Benefits Administration
VBMS:	Veterans Benefits Management Software
VERA:	Veterans Equitable Resource Allocation
Veterans' Choice:	Veterans Access, Choice and Accountability Act
VHA:	Veteran's Health Administration
VHA ORD:	Veterans Health Administration Office of Research and Development

[name] (Research Coordinator), Central Western Mass VA, [name], [contact] [name], Email: [contact]

[name] (Research Coordinator), White River Junction VA, [name], [contact], Email: [contact]

[name] (Research Coordinator), White River Junction VA, [name], [contact], Email: [contact]

[name] (Biostatistician), [name], Department of Psychiatry, Yale School of Medicine. [contact], Email: [contact]

[name] (Collaborator), Palo Alto Veterans Institute for Research, [name], [contact], Email: [contact]

[name] (software developer), Washington DC VA Medical Center, [name], [contact], Email: [contact]

PARTICIPATING STUDY SITES

Hub

- Connecticut VA

Spoke

- Bedford VA
- Boston VA
- Central Western Massachusetts VA
- Maine VA
- Manchester VA
- Providence VA
- White River Junction VA

Other Sites Involved in Data Analysis

- Washington DC VA

PRÉCIS

Study Title

Engaging Veterans Seeking Service-Connection Payments in Pain Treatment

Objectives

Determine the effectiveness and cost-effectiveness of Screening, Brief Intervention and Referral to Treatment for Pain Management (SBIRT-PM) compared to Usual Care (UC) in reducing pain and risky substance use.

Design and Outcomes

In a pragmatic two-arm, parallel groups 36-week multi-site randomized controlled single blind trial, we will randomize 1100 Veterans applying for compensation related to musculoskeletal disorders to either SBIRT-PM or Usual Care (UC) across eight VA medical centers in New England.

Outcome assessment by phone will occur at 12- and 36-week follow-ups and will be corroborated with other sources of information --- the electronic health record and toxicology testing of nail clippings.

Primary outcomes will be change in pain severity as measured by the Brief Pain Inventory (BPI) and change in substances categorized as requiring intervention measured by the ASSIST. Secondary outcomes will include non-pharmacological pain management service utilization, NRS pain severity, pain interference with life activities as measured by the BPI, overall pain (PEG), overall health (EQ-5D-5L), use severity for individual substances generated by the ASSIST, and toxicology results for individual substances. The trial will include cost-effectiveness and budget impact analyses.

Interventions and Duration

Screening, Brief Intervention and Referral to Treatment for Pain Management (SBIRT-PM) aims to engage Veterans applying for compensation with pain conditions in multi-modal non-pharmacological pain care and to motivate those who misuse substances to change this problematic behavior. SBIRT-PM will be delivered centrally by telephone throughout the New England VA Healthcare System's (VISN1) eight medical centers. It involves an initial one-hour session followed by up to three 20-minute calls in a 12-week period and an additional call in the 12-32 week period to support Veterans engagement in non-pharmacological pain care.

Usual care (UC): A Veteran who completes a compensation examination ordinarily has no further treatment, referral or debriefing as part of the Compensation examination

Sample Size and Population

The study sample consists of 1100 randomized post-911 era Veterans applying for MSD related compensation. Participants will be randomized using a computerized urn randomization program within each site to increase the likelihood of balanced allocation of participants to the two interventions on

sex, race, ethnicity and self-reported illicit drug use within 90 days.

1. STUDY OBJECTIVES

1.1 Primary Objective

Our main objective is to test the effectiveness and cost-effectiveness of SBIRT-PM, compared to UC, when delivered within a VISN1-wide hub-and-spoke network.

Objective 1: We will determine if SBIRT-PM is more effective than UC in reducing pain severity as measured by the Pain Severity subscale of the BPI (primary outcome). Secondary outcomes include non-pharmacological pain management service utilization, pain interference with life activities (BPI Interference Subscale), and overall health. Hypothesis: SBIRT-PM will be more effective than UC. We will test the degree to which non-pharmacological pain management service utilization mediates pain outcomes.

Objective 2: We will evaluate if SBIRT-PM, compared to UC, is more effective in reducing the number of substances categorized as requiring any intervention as measured by the ASSIST (primary outcome). Secondary outcomes will include the use severity measure for individual substances generated by the ASSIST, and nail clipping toxicology results for individual substances. Hypothesis: SBIRT-PM will be more effective than UC. We will separately test the degree to which non-pharmacological pain management service utilization and substance use service utilization mediates the effect of SBIRT-PM on substance use outcomes.

Objective 3: We will assess the cost-effectiveness of SBIRT-PM relative to UC. Hypothesis: SBIRT-PM will be cost-effective relative to UC across a range of possible values of decision makers' willingness-to-pay for minimal clinically important differences in pain severity and interference.

1.2 Secondary Objectives

Our secondary objective is to determine if SBIRT-PM is more effective than UC in reducing overall pain as measured by the PEG, a common pain measure required across protocols funded by the NIH-DoD-VA Pain Management Collaboratory, which measures average pain intensity (P), interference with enjoyment of life (E), and interference with general activity (G). Hypothesis: SBIRT-PM will be more effective than UC.

2. BACKGROUND AND RATIONALE

2.1 Background on Condition, Disease, or Other Primary Study Focus

Many Returning Post-9/11 Veterans Have MSD and Could Benefit from Non-Pharmacologic Pain Care.

Military personnel carry heavy packs, move heavy equipment and undergo intense physical stresses; a high proportion of them will develop musculoskeletal disorders (MSD) involving chronic pain. Chronic pain is widely prevalent in Veterans and is one of the most common reasons for outpatient healthcare utilization.¹ In recent years, returning Operation Enduring Freedom (OEF) and Operation Iraqi Freedom (OIF) post-9/11 Veterans with injuries have faced the prospect of decades of chronic pain.^{2,3}

By seven years after deployment, approximately 17.5% of post-9/11 Veterans in VA treatment were diagnosed with back disorders and 17.0% were diagnosed with joint conditions,⁴ higher rates than in comparable U.S. population cohorts.⁵ Back pain, followed by neck or joint pain, is the most common cause of chronic non-cancer pain in Veterans.⁶

To decrease morbidity and mortality, a growing body of research and expert consensus support a multi-modal pain treatment strategy.^{7,8} In this bio-psycho-socially-oriented model, evidence-based non-pharmacologic treatment modalities are incorporated alongside pharmacologic treatment.⁹ Multiple studies have demonstrated the effectiveness of non-pharmacological pain management in improving chronic pain outcomes, including, for example, physical therapy,¹⁰⁻¹² cognitive behavioral therapy,^{13,14} yoga,^{15,16} and mindfulness based stress-reduction,¹⁷⁻¹⁹ and therefore guidelines now stress the importance of a multi-modal approach.^{7,20} In part to reduce prescribing of risky opioids, the availability of such multi-modal therapy at VA facilities was mandated by the 2013 Opioid Safety Initiative.²¹

Veterans with MSD Are at High Risk for Substance Misuse and Need Early Intervention. Veterans²² and other people²³ with painful MSD are at high risk for developing alcohol and other substance use disorders.^{24,25} Iatrogenic factors have contributed to the risk for substance use among Veterans. The opioids prescribed to treat painful MSD carry the potential for aberrant use and eventually misuse. A remarkably high proportion, 64%, of post-9/11 Veterans with *chronic* non-cancer pain have been prescribed opioids,⁶ and Veterans prescribed opioids have worse outcomes than those not prescribed opioids.²⁶ The base rate of substance use disorders in post-9/11 cohorts is high,²⁷⁻³⁰ and baseline substance use is a risk factor for going on to use more substances. The causality is bidirectional, in that substance use disorders predispose people to incurring injuries,³¹ and are overrepresented in Veterans with pain-related comorbidities^{27,32,33}

Early intervention is needed for Veterans who have chronic pain and are at risk for substance misuse or are already engaging in it. Individuals with chronic pain and SUD have worse pain-related outcomes³⁴ and worse addiction-related outcomes,³⁵ than those without comorbid pain, supporting the need to intervene early to prevent this comorbidity. Restrictions on opioid prescribing may come too late to alter the neurobiological changes associated with long-term opioid treatment for chronic pain.³⁶⁻³⁸ These neuroplastic changes endure long after opioid treatment is withdrawn and are thought to play a key role in facilitation of transition to chronic pain. Early engagement of Veterans with chronic pain into multi-modal non-pharmacological treatments has the potential to arrest the development of risky or disordered substance use and help those already misusing substances to reduce or stop this problem behavior. Furthermore, since substance use is strongly associated with treatment non-compliance in numerous settings, early interventions that reduce risky substance use have the potential to improve pain treatment outcomes by increasing Veterans' pain treatment adherence. In this proposal, although measured separately from non-pharmacological pain treatments, substance use treatment is facilitated because it is a component of pain treatment.

2.2 Study Rationale

Compensation Examinations as a Unique Opportunity to Engage Veterans in Multi-modal Pain Care.

As of 2015, there were 971,117 post-9/11 Veterans already receiving service-connected compensation. Many of these Veterans interact with service-connection examiners at VA facilities, but they interact as claimants, not as patients. When Veterans end their military service, and begin the transition to civilian life, they are encouraged to file claims for physical or psychological conditions that may be related to their military service. Veterans are encouraged to file claims during demobilization, at Veterans' resource fairs to publicize services available to Veterans, and at Veterans Service Organizations that offer assistance with the claims process.³⁹ The claim is processed at the VA but does not involve clinical care.

Many of these claims are for MSD. As of 2015, there were 559,999 post-9/11 Veterans being compensated for back or neck conditions, and 596,250 for limitation of flexion in joints (Veterans often have more than one involved body part).⁴⁰ In 2015 alone, 313,052 new Veterans began receiving disability compensation, of whom approximately 31% were under age 35.

Examinations to determine Veterans' compensation are important because: (1) they are often conducted when Veterans are in some degree of pain or crisis associated with their disorder; (2) significant financial remuneration is at stake; and (3) Veterans judged to have a service-connected condition will receive *priority* care at the VA for it, typically for life. The compensation examiner has a responsibility to the agency that decides claims, the Veterans Benefits Administration (VBA), to obtain information so the claim can be adjudicated. Therefore, as in forensic evaluations, compensation examiners are taught to tell Veterans that the purpose of the examination is to evaluate the disability claim and not to provide treatment. Although the examiner's role might be complicated by him/her making a treatment recommendation, having another clinician explain available treatments is not. The failure to offer treatment can be alienating.⁴¹

Considerable public pressure has developed to improve the process of evaluating compensation claims such that this process includes approaches to engage Veterans in treatment. In testimony to the House Committee on Veterans Affairs, Linda Bilmes called for early intervention approaches that interface with the compensation examination process for returning post-9/11 Veterans: "VBA should shift its focus away from claims processing and onto rehabilitating and reintegration of Veterans."⁴² Congressional hearings in June 2011 addressed "Bridging the Gap Between Care and Compensation for Veterans,"⁴³ the very topic of this proposal. One of the witnesses cited our group's editorial advocating engagement of Veterans in treatment when they apply for service-connection.⁴⁴

Motivational Interviewing to Engage Veterans with MSD in Non-Pharmacological Pain Treatment.

Motivational interviewing,⁴⁵ a person-centered, brief psychotherapeutic approach, helps people resolve ambivalence toward positive behavioral change and strengthen their commitment to it.⁴⁶ Multiple meta-analyses have shown that MI improves treatment outcomes across a variety of behavioral domains in both medical and non-medical settings, including for substance use and treatment engagement.⁴⁷⁻⁴⁹ MI can be

delivered in person or by telephone. Telephone-based MI has been used successfully to address substance use and other risky behaviors in a variety of populations.⁵⁰⁻⁵⁶ It has been shown to significantly increase initiation and retention of post 9/11 veterans in both VA and non-VA mental health treatment, with a secondary effect of significantly and durably decreasing their marijuana use.⁵⁷

Notably, MI has been found to effectively improve chronic pain treatment engagement and outcomes, especially when more than one MI session is employed.^{58,59} Specifically, Habib et al⁵⁹ found that a 2-session assessment and feedback intervention based on MI, in comparison to a standard 2-session assessment and educational control interview, significantly improved the rates in which patients with chronic pain attended a series of pain management workshops. Similarly, Friedrich et al⁵⁸ showed that patients with chronic low back pain attended more physical therapy sessions and had reduced disability and pain levels when the physical therapists had been trained to use strategies consistent with MI during the patients' visits. MI is well-aligned with expert recommendations for patient-centeredness and shared decision-making in chronic pain management.⁶⁰⁻⁶³ Furthermore, the VHA National Center for Health Promotion and Disease Prevention has endorsed the use of MI "to elicit and increase Veterans' own intrinsic motivation to participate in healthcare decisions and change health behaviors that are key to improving health and maintaining their well-being."⁶⁴ We propose to use MI to engage post-9/11 Veterans with MSD in multi-modal non-pharmacological pain management treatments. A recent meta-analysis of MI for chronic pain management concluded that MI is a promising approach for promoting engagement in treatments for chronic pain conditions and underscored the need for well-designed randomized controlled trials to determine the effectiveness of MI within musculoskeletal health.⁶⁵

MI-based SBIRT for Pain Management to Engage Compensation-Seeking Veterans with Chronic Pain.

SBIRT is an approach to identify and briefly intervene with patients with risky substance use in settings not typically associated with addiction treatment.^{66,67} The Brief Intervention in SBIRT usually is based on MI. SBIRT is efficacious for reducing unhealthy alcohol^{68,69} and tobacco use,⁷⁰⁻⁷² although less well established for decreasing illicit drug use^{73,74} or improving drinking outcomes for people with severe alcohol dependence.^{75,76} According to our pilot data, most Veterans meeting criteria for the proposed study are likely to have episodic risky drinking rather than drug use and are not likely to have alcohol dependence (see Preliminary Studies section).

Our group developed SBIRT for Pain Management (SBIRT-PM) to promote engagement in multi-modal non-pharmacological pain management among compensation-seeking Veterans with chronic pain. In SBIRT-PM, a clinician meets with the Veteran after the compensation examination to address the presenting MSD complaint. A clinician rather than the compensation examiner delivers SBIRT-PM to allow the Veteran to engage in a confidential discussion without concern about how it will impact the compensation claim. The clinician addresses Veterans' motivation for multi-modal pain care, and explains how pain can be managed using a variety of non-pharmacological pain management services. The clinician spells out how those services can be accessed at VA.

Using permissive language about how pain is commonly self-medicated with substances, the clinician transitions to inquiries about use of prescription and non-prescription substances. The clinician then attempts to motivate Veterans to change their behavior if they are misusing substances. Thus, SBIRT-PM addresses the Veteran's presenting pain complaint first and nascent substance use subsequently.

A Veterans Integrated Service Network Hub-and-Spoke Model of SBIRT-PM Delivery.

The VA often employs the hub-and-spoke model to manage care across a geographically-dispersed healthcare system. The hub-and-spoke model allows for expertise concentrated in specific geographic areas to be available throughout the system. The Veterans Health Administration is divided into 18 geographical regions across the United States called Veterans Integrated Service Networks (VISN). VISNs are organized as hub-and-spoke networks in which a central administration oversees healthcare policy and service delivery of all medical centers in the designated region.⁷⁷ VISN 1 consists of eight VA medical centers and 50 outpatient clinics throughout the six New England states.

We will adopt a VISN1-wide hub-and-spoke network implementation system in which VA Connecticut Healthcare System will serve as the hub for SBIRT-PM delivery in all eight VISN1 medical centers. The hub will be the site for screening and identifying individuals appropriate for SBIRT-PM, delivering the intervention via telephone to Veterans throughout New England, and referring Veterans to site personnel who make pain management service referrals. This approach has the advantage of fitting the way in which many other clinical interventions and areas of expertise are delivered within VA. One widely used example of a hub-and-spoke model in VHA is SCAN-ECHO (Specialty Care Access Networks-Extension for Community Healthcare Outcomes). In these programs, "hubs" with experts in a particular area arrange teleconferences, trainings, and case consultation for providers in "spokes" or satellite sites. VA Connecticut is the site for a SCAN-ECHO program for pain management, and this model appears to be effective. Suggestive evidence of its effectiveness is that providers who participate in the pain SCAN-ECHO program have been significantly more likely to use physical medicine, anti-depressants, and anti-convulsant treatments, but not opioids.⁷⁸ Other examples are the VA Epilepsy Centers of Excellence to assure increased access to high quality of care for Veterans with epilepsy.⁷⁹ A hub and spoke model has the advantage of being more cost-effective compared to no network from a hospital⁸⁰ and societal perspective.⁸¹ Hub and spoke systems allow for full-time personnel to specialize in the intervention and serve multiple sites, rather than requiring training of larger numbers of personnel at many sites.

[figure not shown]
The theoretical framework for implementation of SBIRT-PM in a hub-and-spoke model is Relational Coordination.⁸² Relational Coordination refers to the quality of communication and collaboration across sites and is predictive of a team's or organization's ability to provide high quality care.⁸³⁻⁸⁵ Hub-and-spoke networks function through collaborative relationships between individuals working across sites.⁸⁶ Information must flow effectively between members of the hub-and-spoke sites for care to be timely, coordinated and appropriate for the patient. In this study, we will first explore how relationships among clinical and administrative staff involved in pain care are coordinated at the sites during baseline semi-structured interviews early in the UG3

phase. Informed by what stakeholders tell us, we will then work to build Relational Coordination within our hub-and-spoke network to deliver SBIRT-PM.

Within the VA, there are financial incentives for VISN-wide initiatives, such as the one proposed, that bring Veterans into VA care. The formula for funding each VISN is essentially a capitated model of payment per Veteran, called the Veterans Equitable Resource Allocation (VERA). Each additional patient in the New England VISN generates a mean of \$6500⁸⁷ (the median is considerably lower) and Veterans whose conditions are judged to be connected to their military service are, understandably, the highest priority Veterans for VA facilities to enroll. The VA as an organization depends on enrolling new Veterans as those from prior wars die or move to other regions.

Beyond having the potential to improve care for Veterans applying for compensation for MSD-related claims, to the extent SBIRT-PM results in new Veteran enrollment, it could increase revenue into VISN1 and its medical centers. Therefore, our proposal includes a budget impact analysis, with the prosaic but crucial information as to how SBIRT-PM impacts the VISN bottom line. We will determine the cost and cost-effectiveness of SBIRT-PM because these data provide evidence for SBIRT-PM's value.

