To illustrate the uncertainty associated with ICER point estimates, cost and effect estimates of SBIRT-PM will be bootstrapped (with 2,000 replicates) to produce confidence intervals around the ICERs and to produce CEACs for each outcome measure.¹⁸⁸ CEACs quantify the uncertainty in the cost-effectiveness analysis by showing the probability that the intervention is cost-effective with respect to any given threshold value.¹⁸⁸⁻¹⁹⁰ Intuitively, as the threshold value of a MCID in a given outcome increases, the strategy that produces that effect most efficiently becomes increasingly more likely to be the most cost effective, even though incremental costs are incurred. Similarly, as the threshold value of a MCID in a given outcome decreases, the strategy that has the lowest cost becomes increasingly more likely to be the most cost-effective. Finally, sensitivity analyses will be conducted to determine the robustness of the cost-effectiveness results to alternative assumptions about a wide variety of implementation parameters (e.g., cost of inputs).

Budget Impact Analysis.

To demonstrate the financial feasibility of adopting SBIRT-PM, a budget impact analysis will be conducted. The per-person cost of SBIRT-PM will comprise the cost of delivering the intervention plus the cost of the VA-funded services used by the participant in the SBIRT-PM condition over and above the cost of those used by individuals in UC, minus the yearly patient allocation (VERA dollars) assigned to that participant. The total projected yearly cost to a given medical center of SBIRT-PM will be the per-person cost times the total number of Veterans applying for compensation and pension for a musculoskeletal condition times the expected rate of uptake.

Analyses of NLP Algorithms

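### No interval or scenario analysis is planned for the budget impact, although its per-person cost includes an estimated between-arm difference

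*Combined protocol and SAP*

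**What the plan says.** Section 9.6 describes two economic analyses, one after the other.

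- **Cost-effectiveness.** The plan states that "cost and effect estimates of SBIRT-PM will be bootstrapped (with 2,000 replicates) to produce confidence intervals around the ICERs", together with acceptability curves. It then adds sensitivity analyses on implementation inputs, which it ties to the cost-effectiveness results.
- **Budget impact.** The purpose is stated as "To demonstrate the financial feasibility of adopting SBIRT-PM, a budget impact analysis will be conducted". The per-person cost is the delivery cost, plus VA-funded services in the SBIRT-PM arm "over and above the cost of those used by individuals in UC", "minus the yearly patient allocation (VERA dollars) assigned to that participant". The scale-up reads: "The total projected yearly cost to a given medical center of SBIRT-PM will be the per-person cost times the total number of Veterans" applying for musculoskeletal compensation, "times the expected rate of uptake". No interval, resampling, scenario or sensitivity analysis is named, and uptake is given neither a value nor a range.

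Section 2.2 explains why the analysis is done: new enrollment brings VERA revenue, and the VISN needs to know the net effect on its finances. It puts the mean VERA amount at $6,500 per additional patient and remarks that "the median is considerably lower". It gives no median and no SD.

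**The concern.** The service-cost component of the budget formula is a difference between two randomized arms, so it has sampling error. The plan accepts this for the ICERs and bootstraps them. In the budget formula the same kind of estimate is multiplied by the number of applicants and by uptake, and no precision is asked for. The VERA term adds further error.

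The result is meant to support adoption. If the formula is followed as written, a center or the VISN could receive a projected yearly gain or loss in dollars without being told how well the trial determines it, or how far it depends on an unstated uptake rate and on the way VERA is credited.

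**Working it through.** **Inputs from the documents.** 1100 randomized (section 9.2), with up to 550 initial SBIRT-PM sessions (section 5.4), hence 550 per arm. Mean VERA $6,500 (section 2.2). Service costs over 36 weeks from VA administrative databases (section 3, costs estimation). Projected MSD examinations of post-9/11 Veterans over 32 months: 10,349 in the VISN, 1,448 of them at VA Connecticut (section 3, feasibility).

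**Inputs that are assumptions.** SD of service cost: $2,500 to $20,000. VERA distribution: lognormal, with median $2,000 to $5,000. Enrollment gain: 2 to 15 percentage points. The documents give none of these.

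**The plan's own figure.** There is no numeric budget result to reproduce. The sample size that sets the precision does reproduce: d = 0.25, two-sided alpha 0.025 and power 0.90 give 398 per group (the plan says 400), and 400/0.73 = 548, times 2 = 1096.

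**Step 1: error of the cost difference.** SE = SD × √(2/550); half-width = 1.96 × SE.

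| Assumed cost SD | SE | 95% half-width per person |
|---|---|---|
| $2,500 | $151 | $295 |
| $5,000 | $302 | $591 |
| $10,000 | $603 | $1,182 |
| $20,000 | $1,206 | $2,364 |

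Costs come from databases, so 550 per arm is reasonable. With 400 per arm the range would be $346 to $2,772.

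**Step 2: error of mean VERA.** For a lognormal, SD = mean × √((mean/median)² − 1). With mean $6,500:

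| Assumed median | SD | 95% half-width of the mean, n = 550 |
|---|---|---|
| $5,000 | $5,399 | $451 |
| $4,000 | $8,326 | $696 |
| $3,000 | $12,494 | $1,044 |
| $2,000 | $20,100 | $1,680 |

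**Step 3: can this error decide the sign?**

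(a) *Formula as written, full VERA subtracted.* Combined half-width = 1.96 × √(cost SD² × 2/550 + VERA SD²/550), treating the two terms as independent. For cost SD $5,000 to $20,000 and VERA SD $5,400 to $12,500, this is about $744 to $2,584. A credit near $6,500 exceeds it. So does that credit pro-rated to 36 weeks: 6,500 × 36/52 = $4,500.

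(b) *Only VERA from additional enrollment, the section 2.2 rationale.* A gain of 2, 5, 10 or 15 points is worth 6,500 × gain = $130, $325, $650 or $975 per person. At cost SD $10,000 all four lie inside ±$1,182; a gain of 1,182/6,500 = 18.2 points would be needed to equal it. At SD $5,000 the figure is 9.1 points. At SD $2,500 it is 4.5 points, so gains of 5 points or more exceed the noise.

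**Step 4: scale-up, for illustration.** VISN: 10,349/32 × 12 = 3,881 Veterans a year; at 18% uptake, 699. At cost SD $10,000: 699 × $1,182 ≈ ±$0.83 million a year. VA Connecticut: 1,448/32 × 12 = 543; × 18% ≈ 98; × $1,182 ≈ ±$0.12 million a year. The 18% is the UG3 pilot enrollment rate, used here only as a placeholder for service uptake.

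**The case against.** The strongest reply is that the formula as written leaves little room for the sign to be noise. **A reader might infer that a projected saving or loss could simply be sampling error.** Step 3(a) shows that the documents do not support this without a condition. If every SBIRT-PM participant carries a credit near $6,500, that credit outweighs the error over the range examined. It also follows that setting the error against delivery cost alone would mislead: 699 × $6,500 = $4.54 million, of which $0.83 million is about 18%. This part of the objection stands.

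Other points stand in part:

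- The plan is silent on uncertainty. It does not say that only a point estimate will be reported.
- A reader might infer that the protocol calls VERA strongly skewed, or that skew distorts the total. It says only that the median is well below the mean, without a figure. A budget total properly uses the mean, so skew affects its precision and does not bias it.
- The cost SDs are assumptions. VERA is a revenue allocation, so its spread cannot stand in for the spread of service costs.
- The 18% pilot rate and the earlier trial's 257/1014 (25.3% by division) are research enrollment rates, not uptake of an adopted service.
- The formula projects to one medical center; the VISN total is a sum. No decision rule is attached to the budget impact, and Objective 3 concerns cost-effectiveness.
- Bootstrap replicates of cost are already planned, so the gap is narrow.

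None of this supplies an uncertainty method for the budget impact, and none was found elsewhere in the documents.

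**Conclusion.** The point holds as a gap in method. Section 9.6 scales up a trial-estimated cost difference to demonstrate feasibility and specifies no measure of precision and no scenarios, although the paragraph before it bootstraps the same kind of estimate.

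Its size can only be illustrated: about ±$295 to ±$2,364 per person for assumed cost SDs of $2,500 to $20,000 with 550 per arm, before VERA error and scale-up. The sign is plausibly open if VERA counts only through additional enrollment, or if many participants draw little or no VERA. It is not open if a full credit near $6,500 is subtracted for everyone.

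That dependence is itself a reason for scenarios. The written formula nets off no VERA for the UC arm and sets a yearly allocation against 36-week costs, so the way VERA enters can matter more than sampling error. The primary outcomes are untouched, but the analysis is meant to inform adoption and the repair is cheap, so it should be made.

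**What to change.** In the budget impact paragraph of section 9.6:

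1. Carry the planned 2,000 bootstrap replicates through the budget formula. Resample participants within arm and keep each participant's service cost and VERA together, so that their correlation is preserved.
2. Report the 95% interval and the proportion of replicates with net cost below zero, per medical center and summed for the VISN. Sum within each replicate: if one per-person estimate is applied at every center, its errors add up and do not average out.
3. Add uptake scenarios, labelled as assumptions. The 18% and 25.3% enrollment rates may appear only as illustrations.
4. Add VERA scenarios: full credit for each SBIRT-PM participant, and the SBIRT-PM minus UC difference, each with costs and VERA on the same time horizon. Without these, bootstrapping the unchanged formula could give a high probability of saving that comes from the crediting rule.
5. State any feasibility conclusion together with the interval and the scenario it rests on.

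The cost is a few sentences and a little extra analysis on replicates already planned. It needs participant-level VERA in both arms; the formula already uses it for SBIRT-PM. The drawback is a less certain headline.
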